1. JUSTIFICATION FOR THE STUDY

1.1. POSITIONING OF THE RESEARCH

With the increase in life expectancy among the French population, there has been a rise in the number of patients with fractures of the upper femur (FESF), particularly among the elderly. In France, the number of hospital stays for UEF has been increasing by 0.3% per year since 1998, and the incidence remains predominantly female. The crude incidence rate of UEF was 42.1/10,000 for people over 55 years of age in 2007. UEF mainly affects elderly and very elderly people. There has been a gradual increase in the average age of fracture patients. Again in 2007, patients over 80 years of age accounted for 60% of male patients operated on for FESF and 70% of female patients (1). This is a serious condition, with the risk of death increasing with age. It is 2% in women under 80 during hospitalisation, rising to 8.3% in those over 95. This mortality rate is higher in men, reaching 15% in men over 94 during hospitalisation (1). Longer-term mortality rates vary according to studies, from 14.7% at one year (2) to 46% at one year in patients over 90 years of age (3). However, there has been a gradual decrease in this mortality rate in France, probably due to improved surgical and perioperative care for patients (4).

Anaemia is common in the geriatric population. In a survey of a hospitalised geriatric population, 24% of patients had anaemia, the aetiology of which was iron deficiency in 15% of cases (5). It is also common in surgery, particularly in the perioperative period. In a study of 546 patients with fractures of the upper femur, 40.4% had anaemia on admission and 93.0% had anaemia postoperatively (6).

Postoperative anaemia has multiple causes. It is probably aggravated by rehydration upon admission of patients with fractures (7). There is blood loss associated with the fracture and the formation of a haematoma prior to surgery (8), but also some postoperative occult bleeding: in 546 patients with a fracture of the upper end of the femur, Foss et al. showed that post-operative occult bleeding ranged from 547 to 1473 mL, in addition to the blood loss observed during surgery. Finally, there is a degree of acute inflammatory anaemia secondary to surgery. This inflammatory component is caused by a decrease in progenitor proliferation, a reduced red blood cell half-life and iron retention by macrophages. This retention is mediated by ferritin, which is then increased, and by hepcidin, a recently discovered protein that regulates iron metabolism (9).

Loss of independence, defined as a decrease in the ability to care for oneself, is also significant after a fracture of the upper end of the femur. Of 390 patients over the age of 65 who underwent surgery for an FESF and were analysed by Vochteloos team, nearly half did not regain their previous independence after one year. Only 25% of patients who were mobile without assistance regained their previous independence within three months of surgery. Nineteen percent of patients became bedridden. The most significant risk factors were a low level of previous independence and the occurrence of postoperative confusion (10).

The consequences of a loss of independence in elderly people are manifold (11). It leads to the intervention of outside help for activities of daily living, a change of living arrangements, a change in family relationships, and a risk of abuse by carers. The economic consequences are also significant:

health insurance expenditure for dependent elderly people was around €20.9 billion in 2011 (12). A patient's independence can be analysed in various ways. In the studies cited above, functional independence (walking) was prioritised because it was related to the condition being treated. However, in frail patients, overall independence is a key factor to measure because it affects quality of life and institutionalisation. Two scales can be used to measure this independence: Katz's Activities of Daily Living and Lawton's Instrumental Activities of Daily Living. They take into account the patient's independence in performing daily activities alone or with assistance (washing, dressing, continence, eating, financial management, medication management, etc.).

Anaemia appears to be associated with the independence of patients who have undergone FESF surgery, but few studies have analysed the relationship between post-operative anaemia and rehabilitation, especially in elderly subjects (13). However, it is known that anaemia in hospitalised medical patients is an independent factor in poor functional independence (14,15). There are numerous studies analysing the superiority or otherwise of a strict transfusion protocol (following standard transfusion guidelines) compared to a broader transfusion protocol (transfusing patients below the 10 g/dL threshold). This topic was recently addressed in a Cochrane literature review (16) (6 studies, 2,722 patients), which found no difference in mortality, functional recovery, or post-operative morbidity.

This extensive research is based primarily on five studies attempting to establish a link between anaemia and functional autonomy, each of which used different assessments at different post-operative dates.

- **Lawrence (2003)** retrospectively analysed a cohort of 5,793 patients over the age of 60 from 1982 to 1993. It was shown that the average haemoglobin level during hospitalisation was associated with the walking distance covered upon discharge from hospital ($p < 0.001$ adjusted for age, Activities of Daily Living (ADL), neurological diseases, diabetes, Charlson and ASA comorbidities, beta-blocker treatment) [*no reference to possible transfusions*] (17).
- **Foss's work (2008)** found a link between haemoglobin levels in the first three days post-operatively (487 patients, all ages combined) and patient mobility during those first three days ($p < 0.05$, before any transfusion). Independent risk factors for inability to walk were age over 75, dementia, reduced pre-fracture mobility, the presence of post-operative complications, and haemoglobin below 10 g/dL. Patients were treated according to a specialised perioperative rehabilitation protocol [*surgery within 24 hours, spinal anaesthesia, epidural analgesia for 96 hours postoperatively, oral high-protein supplementation, daily 30-minute physiotherapy sessions from the first day*] (18).
- **Halm (2004)** conducted a prospective observational study of 550 patients over the age of 50. High pre- or post-operative haemoglobin levels were correlated with a reduction in length of hospital stay and readmission rates, but not with motor function scores (ability to walk and climb stairs, at day 60, assessed by telephone interview) [*adjusted for age, sex, pre-fracture functional status, dementia, institutionalisation, transfusion*] (19).
- **Gruson (2002)** showed that anaemia on admission in 395 patients over the age of 65 (from 1991 to 1997) with a femoral neck fracture was correlated with a longer hospital stay and higher mortality at 6 and 12 months. A telephone call at 3, 6 and 12 months allowed for the assessment of an ADL and Instrumental Activities of Daily Living (IADL) score and functional autonomy, which were no different between anaemic and non-anaemic patients [*patients who were previously autonomous, living at home and without cognitive impairment; based solely on anaemia on admission*] (20).

- **Maraldi (2006)** analysed 56,752 patients over the age of 65 hospitalised in geriatrics (medicine sector). The recovery of independence at the end of hospitalisation was less significant in anaemic patients than in non-anaemic patients ($p < 0.001$).

However, to our knowledge, no study has examined the association between the recovery of overall functional autonomy, as measured by ADL, and the post-operative haemoglobin level in the very elderly. The aim of these analyses is to improve our understanding of the loss of autonomy observed post-operatively following FESF, especially in the longer term, in order to manage it as effectively as possible. For example, at the Centre Hospitalier Départemental (CHD) in La Roche sur Yon, it would be interesting to optimise the transfusion protocols adopted within the hospital. There are also patient profiles where functional autonomy, and the resulting quality of life, is more important than mortality alone (in very elderly patients, for example, or those with multiple comorbidities). Furthermore, in our department, anaemia is a factor that limits patient mobility (sitting in a chair, physiotherapy), which probably has consequences for their early and future autonomy. The database could be used to set up interventional studies seeking to limit this loss of autonomy.

In this study, we therefore propose to evaluate the impact of post-operative anaemia on the functional recovery of very elderly patients following surgery for a fracture of the upper end of the femur.

1.2. *BENEFITS AND RISKS FOR THE PEOPLE PARTICIPATING IN RESEARCH*

1.2.1. Benefits

It is hoped that this study will improve understanding of the factors influencing the loss of independence commonly observed following a femoral neck fracture.

The management of post-operative anaemia is not formalised, either in national recommendations or at institutional level. The aim of this study is to improve understanding of the repercussions of post-operative anaemia, but also to derive a standardised management protocol. This protocol must, in particular, determine the transfusion strategy for these fragile patients, in order to reserve blood transfusions for those who need them most, but above all to avoid less useful transfusions.

1.2.2. Risks

No risks related to the protocol are expected for the individuals participating in the research. The patient incurs the usual risks associated with the procedure and possible peri- and post-operative complications, including anaemia and its management, in the target population.

1.2.3. Benefit/risk balance

The research manager classifies this **research** as **non-interventional**, since:

- ✓ All procedures are performed in the usual manner (blood sampling, interventions, etc.).

The research does not involve innovative or obsolete techniques or strategies.

All patient care will be identical to standard practice. In particular, the discharge date will be decided by the physician in charge of the patient, independently of the study, but will be recorded in the patient's file and the research CRF.

Consequently, the specific implementation procedures in the research represent negligible constraints for the person participating in the research. (Article R 1121-3 of the Public Health Code (CSP), Decree No. 2006-477 of 26 April 2006)

The research manager shall therefore submit the study protocol to the South-East I Committee for the Protection of Persons (CPP) Sud-Est I for approval and confirmation of the research's eligibility, in accordance with Article L 1121-1 of the Public Health Code (CSP) as resulting from Laws No. 2004-806 of 9 August 2004 and No. 2006-450 of 18 April 2006 relating to public health policy.

BIBLIOGRAPHICAL REFERENCES

1. Oberlin Ph., Mouquet M.C. Femoral neck fractures in France between 1998 and 2007: what impact does ageing have? *Studies Results*. Apr 2010;723.
2. Kim S-M, Moon Y-W, Lim S-J, Yoon B-K, Min Y-K, Lee D-Y, et al. Prediction of survival, second fracture, and functional recovery following the first hip fracture surgery in elderly patients. *Bone*. June 2012;50(6):1343-50.
3. Jennings AG, de Boer P. Should we operate on nonagenarians with hip fractures? *Injury*. Apr 1999;30(3):169-72.

2. OBJECTIVES AND EVALUATION CRITERIA

2.1. OBJECTIVE AND PRIMARY ENDPOINT

2.1.1. Primary objective

The primary objective is to analyse the relationship between the severity of early postoperative anaemia and functional independence at 6 months postoperatively in elderly patients who have undergone surgery for a fracture of the upper femur.

2.1.2. Primary evaluation criterion

- Haemoglobin level on day 5 post-operatively (considered the post-operative haemoglobin reference level in this study)
 - In the case of patients who received a transfusion postoperatively, the reference haemoglobin level will be the haemoglobin level at the end of hospitalisation
- Change in the Activities of Daily Living (ADL) score pre-fracture and 6 months post-operatively.
A loss of independence will be defined as a decrease of one point or more in the ADL.

The reference value for haemoglobin levels was arbitrarily set at 5 days post-operatively. This is because haemoglobin levels recorded in A&E or on admission to the ward prior to surgery, or immediately post-operatively, may be influenced by factors other than isolated anaemia. Dehydration, present in the emergency department or on admission to the ward before the operation, corrected preoperatively, and postoperative haemodilution due to fluid replacement, cause the haemoglobin level to vary without there being any real deglobulation. We therefore postulate that the haemoglobin level on the 5th postoperative day can serve as a reference.

Confounding factors collected

All confounding factors related to loss of autonomy will be collected:

- Transfusion and number of red blood cell concentrates received

The indication for transfusion is at the discretion of the prescriber. However, it is generally accepted to transfuse patients with haemoglobin levels below 8 g/dL, or below 10 g/dL in cases of ischaemic heart disease or poor clinical tolerance.

- Age
- Gender
- Height, weight, Body Mass Index (BMI) calculation
- Screening for past or present higher brain function disorders
- Screening for major sensory disorders
- Screening for depressive symptoms: Mini Geriatric Depression Scale (MiniGDS)
- Comorbidities assessed using the Cumulative Illness Rating Scale - Geriatrics (CIRS-G)
- ASA score
- Number of medications (per class) taken by the patient (anticoagulants, antiplatelet agents, NSAIDs, anti-osteoporotic drugs, analgesics)

- Lifestyle and living environment
- Severe fractures before and after inclusion
- Other falls during the year
- Protein-energy malnutrition
- Iron deficiency (ferritin < 30 µg/L or CRP > 20 mg/L associated with a transferrin saturation coefficient < 15%)
- Recurrence of falls at 1, 3 and 6 months post-op

2.2. *SECONDARY OBJECTIVES AND EVALUATION CRITERIA*

2.2.1. *Secondary objectives*

The secondary objectives are to analyse:

- the influence of post-operative anaemia:
 - on independence in elderly patients who have undergone surgery for a fracture of the upper end of the femur upon discharge from hospital, at 1 month and 3 months post-operatively
 - on mortality 6 months after surgery
- the progression of post-operative anaemia

2.2.2. *Secondary evaluation criteria*

- Lowest postoperative haemoglobin level recorded on admission to the emergency department, on admission to the ward, on D0 (day of surgery), D1, D3, D5, D10 and D15 (postoperative days).
The severity of anaemia will be defined as follows:
 - greater than 12 g/dL,
 - less than or equal to 12 g/L
 - less than or equal to 8 g/L
 - less than 8 g/dL (and therefore requiring a transfusion)
- Assessment of Activities of Daily Living (ADL): pre-fracture, on day 5 post-operative (or on discharge from hospital if discharged before day 5) at 1 month, 3 months and 6 months post-operative.
- Assessment of instrumental Activities of Daily Living (IADL): pre-fracture, at 1 month, 3 months and 6 months post-operative.
Loss of independence will be defined as a decrease of one point or more in the ADL and/or IADL.
- Vital status at 6 months post-operatively

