Record of falls occurring during hospitalisation

Record transfusions and number of red blood cell concentrates Measure haemoglobin levels on days 1, 3, 5, 10 and 15 after surgery

Recording of Venofer® administration on day 5 (or on discharge if this occurs before day 5)

Recording of post-operative complications: post-operative infection requiring antibiotic therapy (surgical site, pulmonary, urinary, skin, other), acute urinary retention requiring catheterisation, dislocation/loosening of prosthesis, iron deficiency (ferritin < 30 µg/L or CRP > 20 µg/L)

requiring urinary catheterisation, dislocation/loosening of prosthesis, iron deficiency (ferritin < 30 µg/L or CRP > 20 mg/L associated with a transferrin saturation coefficient < 15%) and/or vitamin deficiency (B12 < laboratory threshold, B9 (folate) < 3.5 ng/mL), cardiovascular/neurological complications, post-operative bleeding (including local and digestive), reoperation, haematomas.

Prescription for haemoglobin monitoring on days 5, 10 and 15 post-operatively if the patient has been discharged from hospital

Time allowed for completion: +/- 2 days

c. At the end of hospitalisation: (investigator)

Number of medications (by class) (anticoagulants, antiplatelet agents, NSAIDs, anti-osteoporotics, analgesics)

Screening for current higher brain function disorders Record of length of hospital stay

Record of discharge status

Record of vital status

d. Follow-up telephone call 1 month and 3 months post-operative (supplemented if necessary by questioning the patient, family or nursing home staff)

Record of living arrangements and location

Completion of ADL and IADL

questionnaires Completion of CAS

questionnaire

Investigation of late post-operative complications: infection requiring antibiotic treatment (surgical site, pulmonary, urinary, skin, other), acute urinary retention requiring urinary catheterisation, dislocation/loosening of prosthesis, cardiovascular/neurological complications, reoperation.

Record of recurrent falls or fractures New

hospitalisation and reason for hospitalisation Record of

vital status

e. Telephone follow-up 6 months post-operative (supplemented if necessary by questioning the patient, family or nursing home staff)

Record of lifestyle and living arrangements

Completion of ADL and IADL questionnaires

Completion of CAS questionnaire

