- **Record of transfusions** and number of red blood cell concentrates administered.

- Occurrence of **cardiovascular complications**: deep vein thrombosis, pulmonary embolism, myocardial ischaemia (increased troponin).

- Occurrence of a **neurological complication**: stroke, cerebrovascular accident, etc.

- **Post-operative bleeding** (including localised bleeding and gastrointestinal bleeding)

- Need for **repeat surgery**

- Occurrence of **haematomas**

- **Record of falls**

- **Vital status**

Post-operative M1, M3 and M6:

- Occurrence of **infection** (surgical site, pulmonary, urinary, skin, other), requiring antibiotic therapy.
- Occurrence of **acute urinary retention** requiring urinary catheterisation
- Occurrence of **dislocation/loosening of prosthesis**
- Occurrence of a **cardiovascular complication**: deep vein thrombosis, pulmonary embolism, myocardial ischaemia (increased troponin)
- Occurrence of a **neurological complication**: stroke, etc.
- Need for **repeat surgery**
-
- Record of recurrent **falls or fractures**
- Record of **new hospitalisations** and reasons
- **Vital status**

e. On geriatric assessment

- **CIRS-G(28) scale (in-hospital - inclusion):**

This is a comorbidity scale frequently used in studies because it provides a description of the health status of a population, describing chronic conditions and diseases that have an impact on autonomy, with good reliability and reproducibility

(29). For 14 major systems or groups of systems (cardiac, vascular, pulmonary pathologies, etc.), a score out of 4 is given: 1 being a mild pathology (chronic sinusitis or smoking less than 20 pack-years, for example), 4 is a severe condition causing disability or requiring immediate treatment (acute urinary retention or stroke with hemiparesis).

- **ASA score (30) (in-hospital - inclusion)**

Scale used in anaesthesiology Classifying patients into 6 categories: 1: healthy patient,

2 : with moderate impairment of a major function,

3 : patient with severe impairment of a major function that does not result in disability,

4 : patient with severe impairment of a major function, which is disabling and life-threatening,

5 : moribund patient,

6 : patient declared brain dead whose organs are being harvested for transplantation.

- Screening for depressive symptoms: **MiniGDS** score (*intra-hospital – inclusion*).

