4.4. SPECIAL SITUATIONS

Dementia patients: the interview with dementia patients will be completed by their family or nursing home staff. Information about participation in the study will be provided to the family/trusted relative.

If surgery is postponed (due to the patient's general condition or the presence of antiplatelet or anticoagulant treatment, for example), D0 remains the date of the procedure and corresponds to the patient's return to the orthopaedic/orthopaedic surgery department (after the procedure).

If the patient is discharged early, a standardised prescription will allow haemoglobin to be monitored on D5, D10 and D15 (timeframe: +/- 2 days).

A patient may receive a transfusion,

- pre- or peri-operative transfusion in the recovery room
- post-operative transfusion
 - In hospital: during the orthopaedic stay
 - Post-hospital: new hospitalisation required for transfusion

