5.2.1. Description of methods planned planned, including the schedule for planned interim analyses

All variables collected will be described by minimum, maximum, quartiles, mean and standard deviation for quantitative variables and by number and percentage of each modality for qualitative variables.

Analysis of the primary endpoint:

The relationship between loss of independence at 6 months and post-operative anaemia will be analysed using a logistic model. If a link is found, a multivariate analysis will be performed to confirm the independence of the anaemia/independence relationship. To do this, all potential confounding factors will be tested in a univariate analysis. Factors associated with a p value <0.20 will be retained in the multivariate model.

Analysis of secondary criteria:

- The analysis of the relationship between loss of autonomy on day 5 (or on discharge from hospital if discharged before day 5), at 1 and 3 months, and post-operative anaemia will be performed using the same method as for the primary endpoint.
- The 6-month mortality rate will be estimated with its 95% confidence interval using the Kaplan-Meier method.

The association between anaemia and mortality at 6 months will be studied using a Cox proportional hazards model in order to take confounding factors into account.

- The progression of post-operative anaemia (D0 to D15) will be described graphically.

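### The reference haemoglobin is defined differently for patients transfused after surgery, yet the primary analysis does not guarantee adjustment for transfusion, so the crude odds ratio that decides whether any adjustment follows can be distorted

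*Combined protocol and SAP*

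**What the plan says.** Section 2.1.2 takes Hb on post-operative day 5 as the reference, with one exception: for a patient transfused after the operation, "the reference haemoglobin level will be the haemoglobin level at the end of hospitalisation". The list of confounders in the same section opens with "Transfusion and number of red blood cell concentrates received". The section leaves the indication to the prescriber but notes that "it is generally accepted to transfuse patients with haemoglobin levels below 8 g/dL, or below 10 g/dL in cases of ischaemic heart disease"; poor clinical tolerance is a further reason.

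On timing, section 1.2.3 says that "the discharge date will be decided by the physician in charge of the patient, independently of the study". Section 4.1(b) instructs staff to "Measure haemoglobin levels on days 1, 3, 5, 10 and 15 after surgery", and section 4.1(c), on the end of the stay, lists no Hb sample. Section 4.4 includes among post-operative transfusions "Post-hospital: new hospitalisation required for transfusion".

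Section 5.2.1 gives the primary analysis as a logistic model of 6-month loss of independence on post-operative anaemia and names no covariates. It continues: "If a link is found, a multivariate analysis will be performed to confirm the independence of the anaemia/independence relationship". Each potential confounder is first tested alone and enters only if its p-value is below 0.20. Loss of independence on day 5, at 1 month and at 3 months is to be analysed in the same way. No section forces transfusion into the model, stratifies by it, or plans a sensitivity analysis with another Hb.

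**The concern.** The exposure is measured by one rule in untransfused patients and by another in transfused patients, and low Hb is a main reason for being transfused. Many of the most anaemic patients are therefore entered at a later and usually higher Hb, on a date that depends on when they go home. Transfusion also marks its own indication (heart disease, poor tolerance), which may predict loss of independence. For the exposure as written, transfusion thus determines how Hb is measured and may be related to outcome. It is not an optional covariate.

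The crude model ignores this, and its result decides whether any adjusted model is fitted. If the crude association is diluted, the plan stops there. If it arises from transfusion or its indication, a spurious crude result is reported before any adjustment. This matters because section 1.2.1 intends to derive a transfusion strategy from the study, which requires Hb to be separated from transfusion.

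A smaller problem affects the secondary day-5 analysis. For a transfused patient who stays beyond day 5, the end-of-stay Hb is measured after the outcome it is meant to explain.

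**Working it through.** **1. The plan's own figures (section 5.2.2).** 320 × (1 − 0.10 − 0.10) = 256, and 210 × 1.5 × 0.9 × 0.9 = 255.15, so the stated 255 reproduces. Expected events: 255 × (1 − 0.678) = 82.1. At ten events per term, 82.1 / 10 allows about 8 terms. The 32.2% is the cited 12-month figure applied to a 6-month endpoint.

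**2. Mechanism.** Suppose pre-transfusion Hb drives outcome with OR 1.3 per g/dL lower. A patient at 8 g/dL who rises by 2 has a reference Hb of 10, but has 1.3² = 1.69 times the odds of an untransfused patient at 10. The crude model treats the two as alike. A transfusion term absorbs the constant gap, 2 × ln 1.3 = 0.52 on the log-odds scale, and leaves the slope within each group to estimate the Hb effect.

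**3. Simulation inputs.**
- From the documents: n = 255; 32.2% events; 65% with Hb below 10 g/dL (section 5.2.2); test at 5% (section 5.2.3).
- Assumed: Hb analysed as continuous (section 5.2.1 says only anaemia); normal distribution with SD 1.2 or 1.5; true OR 1.3 per g/dL lower; all patients below 8 g/dL, and 20% or 40% of those at 8-10 g/dL, transfused; end-of-stay Hb equal to the earlier value plus 1, 2 or 3 g/dL, or close to 9.5 or 10.5. This gives 2 × 2 × 5 = 20 settings.
- Implied: with SD 1.2 the mean is 10 − 0.385 × 1.2 = 9.54, about 10% lie below 8 and 55% at 8-10, so 10 + 0.2 × 55 = 21% are transfused. With SD 1.5 and the 40% rule the share is 36%.

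**4. Results, written reference Hb.** OR is per g/dL lower.

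| Truth | Crude OR | OR with transfusion in model |
|---|---|---|
| Pre-transfusion Hb drives outcome, OR 1.3 | about 1.1 to 1.34 | 1.25 to 1.30 |
| Post-transfusion Hb drives outcome, OR 1.3 | 1.30 to 1.31 | 1.30 to 1.32 |
| No Hb effect, transfused odds doubled | 0.85 to 1.10 | about 1.0 |

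Power with the pre-transfusion driver is 11-76% crude and 29-58% with transfusion forced in. With the post-transfusion driver it is 43-70% and 42-64%.

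**5. The p<0.20 screen.** From a two-proportion power calculation at alpha 0.20, n = 255, 32.2% events and 20-50% transfused, transfusion is dropped with probability 67-72% if its OR is 1.25, 41-51% if 1.5, and 10-20% if 2.0.

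**6. The whole two-step rule when Hb has no effect.** With transfused odds multiplied by 1.5 to 2, the crude test alone rejects in 4-31% of trials. Counting a claim only when the crude test is significant and Hb stays significant in the screened multivariate model, the rate is about 1-6%, against 3-7% with transfusion forced in.

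**7. Transfusion directed by comorbidity.** Here 20% or 40% of patients are comorbid, with OR 1.5 or 2 on outcome; 70% or 100% of comorbid patients and 10% of others at 8-10 g/dL are transfused (22-39% overall); rises are 1, 2 or 3 g/dL. For a true OR of 1.3 the estimates are 0.92-1.32 crude, 1.13-1.27 with transfusion alone, and 1.26-1.32 with transfusion and comorbidity. This is the reason for adding CIRS-G, which section 4.3(e) presents as "describing chronic conditions and diseases that have an impact on autonomy". If comorbidity is measured by a proxy with 80% sensitivity and specificity, the estimate is 1.16-1.27, so some bias remains.

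**The case against.** **The final error rate is not inflated.** A reader might infer from step 6 that the plan carries a false-positive rate of 4-31%, or up to 59% if 255 is scaled to the 42-month inclusion period (255 × 42/18 = 595). The documents do not support that, because section 5.2.1 treats the crude result as needing confirmation. Where crude rejection peaked at about 30%, transfusion passed the screen in 96% of the crude-positive trials. With comorbidity-directed transfusion and both factors screened, the two-step rule gave 0-5% (forced 3-7%); with the imperfect proxy, 3-10% (forced 3-11%). This objection stands in full.

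**Forcing does not reliably raise power.** In the first set of 20 settings it lowered power below crude in 9 with the pre-transfusion driver and in all 20 with the post-transfusion driver, mostly by small amounts. This also stands. In some settings with the pre-transfusion driver, such as a 3 g/dL rise, real signal is lost at the crude step and forcing helps. That gate affects every confounder; it is raised here only because the exposure definition distorts the estimate on which it acts.

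**The exposure is a legitimate choice.** Whether pre- or post-transfusion Hb is of interest is a question of estimand, and section 2.1.2 gives reasons for distrusting immediate post-operative values. The written reference Hb is not disputed. Nor is transfusion ignored: it is collected and would be screened if a crude link appeared.

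**The wording gaps are small.** With Hb scheduled up to day 15, the last in-stay value is the natural reading of the end-of-stay level. A transfusion on readmission would, read literally, displace a day-5 value that predates it, but the index end-of-stay Hb predates it too. Both are clarifications only.

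**Conclusion.** The point holds as one of bias in the crude estimate and of adjustment that is not guaranteed. The reference Hb depends on transfusion, and the plan can stop at an odds ratio that mixes the two. Under the stated assumptions a true OR of 1.3 appears as about 1.1 to 1.34 when pre-transfusion Hb drives outcome, and a null effect as 0.85 to 1.10 when transfused patients have doubled odds. Including transfusion brings these to 1.25-1.30 and about 1.0. If post-transfusion Hb drives outcome, the crude estimate is essentially unbiased in the first set of settings.

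The direction and size rest on the transfused share, the Hb rise, the Hb SD and which Hb matters for 6-month independence, none of which the documents give. Neither an inflated final false-positive rate nor a general loss of power is supported. The change is worth making because transfusion is a confounder the protocol itself names, it determines how the exposure is measured, and it is already collected. Confidence is medium.

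**What to change.** 1. In section 5.2.1, make the primary analysis a logistic model of the written reference Hb that always contains post-operative transfusion (yes/no) and the CIRS-G score, whatever the crude result and whatever their univariate p-values. Report the crude model alongside.
2. Add a sensitivity analysis using day-5 Hb for all patients, stating that this value is also post-transfusion for those transfused before day 5. An analysis on the last Hb before transfusion would need transfusion dates. Sections 4.1 and 4.3 list only transfusions and units, so it should not be relied on.
3. For the secondary day-5 ADL analysis, use no Hb measured after that ADL.
4. As clarifications, state in section 2.1.2 that the end-of-hospitalisation value is the last Hb of the index stay, and say how a transfusion on readmission is handled.

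**Cost.** Wording in sections 2.1.2 and 5.2.1 and some extra analysis; no new sample or visit, and no change to transfusion practice. Two terms are spent on about 82 expected events. The standard error of the Hb coefficient rises by 0-26% with transfusion in the model, so power falls in some settings. CIRS-G captures the indication for transfusion imperfectly, so residual confounding by indication remains and should be acknowledged in the report.
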